# Human Subjects Research Protocol

The Common Human Subjects Protocol Cover Form **must** be completed and accompany this form. This Protocol form should be completed for any human subjects research proposal that does not have a specific "protocol," such as a grant application. This form must be submitted along with a copy of the complete grant proposal and all the information in this form **must** be consistent with that proposal. This protocol form, once IRB approved, will be the working protocol for that research. **When completing this document, do not refer to page numbers within your grant.** If revisions are necessary during the course of the research, amendments should refer to this protocol form, not the grant proposal. Enter responses for all sections. Check N/A if the section does not apply. All materials must be submitted electronically to the IRB via InfoEd. Proper security access is needed to make electronic submissions. Visit the [InfoEd Resource Materials](#) page for more information.

## PROTOCOL SUMMARY

Project Title:

Protocol Version Date:

MitoQ for the treatment of Metabolic Dysfunction in Asthma

07/13/2022

Principal Investigator: [name]

Grant Sponsor: NIH

Grant Number: HL137619

(For grants routed through UVM, indicate the OSP Proposal ID # located at the top of the OSP Routing Form)

**Lay Language Summary:** (Please use non-technical language that would be understood by nonscientific IRB members to summarize the proposed research project. The information must include: (1) a brief statement of the problem and related theory supporting the intent of the study, and (2) a brief but specific description of the procedure(s) involving the human subjects. Please do not exceed one single-spaced 8 1/2 X 11" page.)

This study will be a 14-week, randomized, placebo-controlled, double-masked clinical trial in 40 obese patients with poorly controlled asthma.

The intervention is Mitoquinol (MitoQ), which is an antioxidant oral supplement.

The primary aim of this pilot study is to determine if MitoQ improves airway reactivity in obese patients with asthma.

Procedures involved in this study include randomization to MitoQ versus placebo, lung function testing, collection of blood, sputum, exhaled breath, questionnaires (pertaining to general health and asthma), collection of nasal cells, nasal strip, and nasal lavage.

## PURPOSE AND OBJECTIVES

**Purpose:** The importance of the research and the potential knowledge to be gained should be explained in detail. Give background information.

Nearly 60% of patients with severe asthma in the U.S. are obese. Obese asthmatics do not respond as well to standard therapy as lean asthmatics. Obese asthmatics with earlier-onset disease and increased markers of inflammation tend to have the most severe asthma, with a 6-fold risk of ICU admission compared with lean asthmatics. Therefore, there is an urgent need to find therapies for these patients.

The mechanisms causing asthma in obesity remain unclear, but we have data suggesting it might relate to mitochondrial dysfunction. This trial will study the efficacy of targeting mitochondrial reactive oxygen species (mROS) for treatment of obese asthma using a mitochondrial targeted antioxidant, MitoQ.

MitoQ has been extensively studied in animal models of disease, with efficacy in models of Parkinson's disease, sepsis, steatohepatitis, ischemia-reperfusion injury, and diabetic kidney disease. Based on these studies, the efficacy of MitoQ has also been investigated in human diseases. For example, in one study 128 patients with Parkinson's Disease were enrolled in a 3-arm, randomized, double-masked trial of two doses of MitoQ compared with placebo over 12 months. The drug was well tolerated; the only significant side-effect being a dose-dependent risk of nausea and vomiting. The intervention did not have clinical efficacy in this patient population, likely because participants already had established, irreversible, neurologic injury. In a separate study of hepatitis C (involving 30 participants), MitoQ was found to reduce serum alanine transaminase and aspartate aminotransferase, and markers of acute inflammation. Combined, these studies support the safety of MitoQ for use in humans, and suggest potential efficacy in disease with active inflammation related to mROS, such as obese asthma.

We have preliminary data in a mouse model of house dust mite (HDM)-induced airway disease indicating that administration of MitoQ decreases airway inflammation and airway hyperresponsiveness to methacholine. Hence, MitoQ is an exciting potential therapy for the treatment of obese asthma.

#### Primary Outcome

The primary outcome will be change in airway reactivity, based on our preliminary data suggesting that MitoQ affects airway reactivity.

### Secondary outcomes

- ◆ Change in mitochondrial reactive oxygen species in nasal epithelial cells.
- ◆ Change in sputum, nasal lavage, serum and exhaled breath 8-isoprostanes.
- ◆ Change in induced sputum cell counts.
- ◆ Changes in asthma control documented with daily asthma diaries (including symptoms, rescue medication use, and peak flow measurements).
- ◆ Adherence monitored in daily asthma diary cards and by pill counts.
- ◆ The Asthma Control Test (ACT), a 4-week recall questionnaire that measures asthma control.
- ◆ The Marks Asthma Quality of Life Questionnaire (Marks AQLQ), an asthma-specific quality of life questionnaire.
- ◆ The Asthma Symptom Utility Index (ASUI), a 2-week utility-weighted asthma symptom questionnaire.
- ◆ Anthropometrics will include height and weight, and hip and waist measurements.
- ◆ Spirometry with bronchodilator will be performed to measure FEV1 and FVC in accordance with ATS/ERS standards.
- ◆ Forced oscillation (with methacholine testing) will be used to measure impedance, detect changes in the periphery of the lung.
- ◆ Adverse effects will be assessed by open-ended questions at each visit and rated in severity.
- ◆ Interval health history will be recorded at each clinic visit.
- ◆ Baseline questionnaires and exam will be administered to ascertain demographics, including self-reported ethnicity and race, general health, co-morbid conditions, asthma symptoms, and medication use.
- ◆ Exit questionnaires will be administered at the last visit to determine global assessments of treatment, adequacy of informed consent procedures, satisfaction with study procedures and personnel, and opinions about the intervention.

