Drug return/ Pill counts				*	*		*
Assess for adverse events		*	*	*	*	*	*
Spirometry	*¥	* €				*€	*€
Forced oscillation	*	*				*	*
Lung Volumes	*						
Induced sputum	*					*‡	
Exhaled breath condensate	*	*					*
Exhaled nitric oxide	*	*					*
Methacholine Challenge		*^					*
Nasal lavage & nasal brush	*	*					*
Nasal strip	*	*				*	*
Asthma Control (ACT)	*	*		*	*		*
Marks AQLQ	*	*		*	*		*
ASUI	*						
Anthropometrics	*	*		*	*		*
Temperature	*	*					*
Blood pressure	*	*				*	*
Blood draw†	*	Fasting		Fasting	Fasting	Fasting	
Urine sample	*	*		*	*	*	*
Pregnancy test*	*	*		*	*	*	*
Follow-up phone call			*				
End of study questionnaire							*
Follow-up visit+	*	*				*	*

\*for women of child-bearing potential

¥V1 spirometry only will be performed pre and post bronchodilator

†fasting blood draw may be performed on a different day ( $\pm 7$  days of actual visit)

‡Induced sputum at V5 will be performed within 10 days prior to the other V5 procedures (induced sputum and methacholine cannot be done at same visit, both may cause bronchoconstriction)

^participants with a negative methacholine test will stop visit 2 early

†follow-up visits will be scheduled in the event that a lung test cannot be performed that day

€ spirometry is done as part of the induced sputum or methacholine procedure

∞Visit windows for the visits following visit 2 will be scheduled based off of the date the participant was randomized to study drug

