#### Visit 1 (duration three to four hours)

We will obtain informed consent, a baseline medical history, concomitant medications, and measure blood pressure, temperature, height, weight, and waist and hip circumference. We will collect urine for research. Women of childbearing potential will perform a urine pregnancy test. Participants will have blood drawn for an IgE, CBC w/ differential, CMP, and collection of serum and plasma for research. We will perform spirometry with bronchodilator, lung volumes, forced oscillation, and then induce sputum spontaneously or with inhaled hypertonic saline. We will collect exhaled breath condensate and exhaled nitric oxide measurement. We will insert a nasal strip for sample collection, then perform nasal lavage, and collect nasal cells via nasal brush. Participants will complete questionnaires pertaining to asthma control and asthma quality of life. We will instruct participants how to fill out asthma diary cards.

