#### Visit 2 (duration 2 to 3 hours)

Participants will have fasting blood drawn for blood glucose, CBC w/ differential, CMP, and collection of serum and plasma for research (this may also be scheduled within 7 days per participant preference), assess for adverse events, obtain weight, measure blood pressure, temperature, review concomitant medications, obtain interim medical history, collect and review diary cards, perform spirometry, and perform a methacholine challenge test (measuring response by both FEV1 and forced oscillation). If we are unable to obtain sputum from the participant at visit 1 we will see if the participant is able to produce sputum spontaneously during pulmonary function testing. We will collect urine for research. Women of childbearing potential will perform a urine pregnancy test. We will collect exhaled breath condensate and exhaled nitric oxide measurement. We will insert a nasal strip for sample collection, then perform nasal lavage, and collect nasal cells via nasal brush. Participants will complete questionnaires about asthma control and asthma quality of life. Participants will be randomized to study medication and study drug will be dispensed.

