#### Visit 5a (duration 1.5 hours)

We will schedule the induced sputum prior to other study procedures (within 10 days of V5). We will assess for any adverse events, measure blood pressure, perform forced oscillation, obtain spontaneous sputum or perform the induced sputum procedure, review concomitant medications, and obtain an interim medical history. We will insert a nasal strip for sample collection. We will collect urine for research. Women of childbearing potential will perform a urine pregnancy test. Participants will have fasting blood drawn for

blood glucose, CBC w/ differential, CMP, and collection of serum and plasma for research (this may also be scheduled within 7 days per participant preference).

Visit 5b (duration 3 hours)

We will collect and review diary cards and assess adherence to study medication (by pill count). We will collect all remaining study drug. We will perform nasal lavage, collect nasal cells via nasal brush, measure blood pressure, temperature, obtain weight, and hip and waist circumference. Participants will perform spirometry. We will insert a nasal strip for sample collection. We will collect urine for research. Women of childbearing potential will perform a urine pregnancy test. We will perform a methacholine challenge test with forced oscillation (measuring response by both FEV1 and forced oscillation). If we are unable to obtain sputum from the participant at visit 5a we will see if the participant is able to produce sputum spontaneously during pulmonary function testing. We will collect exhaled breath condensate and exhaled nitric oxide. Participants will complete questionnaires about asthma control and asthma quality of life, and an end of study participant questionnaire.

Additional visit:

Some participants may be asked to return for an additional visit if some of the tests were not completed at the regular scheduled visits or for unexpected events. This additional visit may involve spirometry, a methacholine challenge, or induced sputum depending on the need for the specific participant. The participant's blood pressure will be assessed if the methacholine challenge or induced sputum need to be performed. In addition, women of childbearing potential will be required to undergo a urine pregnancy test prior to testing.

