**Sample size.** The sample size calculations are based upon estimates of clinically meaningful mean differences and standard deviations derived from our studies of obese asthmatics at the University of Vermont (although this is predominantly a Caucasian population compared with the Duke site, we have found that methacholine reactivity variability does not differ by race [or BMI] in prior studies of the ALA-ACRC). The analysis is based upon a repeated measures analysis of variance approach. The primary outcome is the methacholine responsiveness. We assume that after treatment with MitoQ, a 20% fall in FEV1 will be detected using a mean methacholine dose of 4 mg/ml, an improvement over the baseline estimate of 2 mg/ml. It is assumed that those in the control group will show no improvement over baseline. Using a within-person standard deviation of 3.0, and the assumptions indicated above, 17 individuals per group would provide 80% power with a 5% significance level to detect a difference between patients assigned to active treatment versus placebo. We will inflate these numbers to allow for a 10% patient drop-out and plan to recruit 40 participants total. Pre- and post- changes in mean lung function (% predicted) and questionnaire scores will be compared for each group, and across groups as described previously.

**Data quality.** Data Quality will be enforced through a variety of techniques, and in collaboration with [name] in biostatistics at UVM. This includes the preparation of a detailed manual of operations, staff training and certification of key staff in study procedures, design of unambiguous self-documenting data collection forms, double data entry, audit of source documents against the central database, automated intra-form and inter-form data consistency checks, range and validity checks during data entry, and centralized eligibility checks and randomization assignments. We will have an in-person training meeting at the start of this clinical study for the Investigators and Coordinators at Duke and UVM.

Data quality will be reviewed and discussed at monthly conference calls. [name] will meet in person no less than three times a year at the Steering Committee meetings of the American Lung Association-Airways Clinical Research Center network.

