### **Reporting Mechanisms of IRB actions to NHLBI**

Routine IRB actions will be summarized in annual reporting to the IRB.

IRB actions that involve significant safety issues will be reported to NHLBI within 15 days of the action.

***Withdrawal Procedures:*** Define the precise criteria for withdrawing subjects from the study. Include a description of study requirements for when a subject withdraws him or herself from the study (if applicable).

Participants may withdraw at any-time, we will ask the participant to consider completing questionnaires regarding asthma control, and quality of life and end of study questionnaire if they withdraw prior to the end of the study.

A study participant will be discontinued from the study for:

- Any clinical adverse event, clinically significant laboratory abnormality, intercurrent illness, other medical condition or situation occurs such that continued participation in the study would not be in the best interest of the participant in the opinion of the site investigator.
- Development of any exclusion criteria may be cause for discontinuation.
- Stops corresponding with study staff team, i.e., “lost to follow-up”. Participants will be contacted at least three times by either e-mail or phone. These contact attempts will be recorded by study personnel. If the participant does not respond after the third attempt, they may be withdrawn from the study and considered “lost to follow-up”.

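### The ASUI is listed as a secondary outcome, but the visit schedule marks it only at V1, before randomization, so following the schedule yields no post-treatment value to analyse

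*Combined protocol and SAP*

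**What the plan says.** - **Outcome list (Secondary outcomes).** The ASUI has its own entry: "The Asthma Symptom Utility Index (ASUI), a 2-week utility-weighted asthma symptom questionnaire". It follows the entries for the ACT and the Marks AQLQ.
- **Schedule (Outline of Study Visits table).** There are seven contact columns: V1, V2, phone call, V3, V4, V5a and V5b. The ACT and Marks AQLQ rows are each marked at five of them. The ASUI row is marked at V1 only.
- **Timing of treatment (Visit 2).** At week 0, "Participants will be randomized to study medication and study drug will be dispensed".
- **Visit text.** Visit 1 says "Participants will complete questionnaires pertaining to asthma control and asthma quality of life". Visit 5b says "Participants will complete questionnaires about asthma control and asthma quality of life, and an end of study participant questionnaire". Visits 2, 3 and 4 use similar general wording.
- **Early withdrawal (Withdrawal Procedures).** The request is equally general: "we will ask the participant to consider completing questionnaires regarding asthma control, and quality of life and end of study questionnaire if they withdraw".
- **Analysis (end of the Sample size paragraph).** "Pre- and post- changes in mean lung function (% predicted) and questionnaire scores will be compared for each group, and across groups as described previously".

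**The concern.** An outcome needs at least one measurement after randomization before it can say anything about treatment. The outcome list treats the ASUI as a companion to the ACT and the Marks AQLQ, and the analysis text covers questionnaire scores without exception. The schedule, which is what coordinators at two centers will work from, asks for the ASUI only two weeks before treatment starts.

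At stake is one listed secondary outcome, the only listed questionnaire described as utility-weighted, in a pilot intended to inform a decision about a larger trial. Scores not collected during treatment cannot be recovered later. The outcome would have to be dropped or its absence explained when the trial is reported.

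**Working it through.** No figure in the plan needs reproducing here. The check is a reading of the schedule against the outcome list, the visit text and the analysis text.

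**1. Count the scheduled collections.** Each of the three questionnaire rows has seven cells, matching the seven columns of the header.

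| Instrument | Scheduled at | Total | After randomization at V2 |
|---|---|---|---|
| ACT | V1, V2, V3, V4, V5b | 5 | 3 (V3, V4, V5b) |
| Marks AQLQ | V1, V2, V3, V4, V5b | 5 | 3 (V3, V4, V5b) |
| ASUI | V1 | 1 | 0 |

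The rows are adjacent and complete, so damage to the table in reading the PDF is an unlikely explanation. The table does mark repeat collection for the two neighbouring instruments.

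**2. Turn this into available data.** With 40 randomized and no losses, the schedule provides 40 × 3 = 120 post-randomization scores for the ACT, the same for the Marks AQLQ, and 40 × 0 = 0 for the ASUI. The number of participants with an ASUI change score is 0 of 40.

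**3. Set this against the analyses.**
- The pre-post comparison of questionnaire scores needs a pre and a post value. The ASUI has no post value.
- A comparison of arms at the end of the study needs a value at V5b. None is scheduled.
- The mixed models in the Analysis Plan need follow-up observations. There are none.
- Multiple imputation, the Analysis Plan's remedy for missing data, has nothing to work from when no participant in either arm has an observed post-treatment value.

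**4. Look for collection elsewhere.** The visit descriptions name none of the three instruments at any visit, including the ACT and the Marks AQLQ. Their general wording is nearly the same at V1, where the table does mark the ASUI, as at the later visits, where it does not. The text therefore neither confirms nor excludes later collection. The withdrawal request is general in the same way. The table is the only place that assigns the ASUI to a visit.

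**5. Check the timing of the one value.** V1 is at week -2. With two-week recall, a V1 score covers roughly weeks -4 to -2. A V2 score would cover roughly weeks -2 to 0, the run-in immediately before treatment. This matters only once a follow-up value exists, but it is the reason to choose V2 as the baseline.

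**The case against.** **The ASUI may be a baseline descriptor.** The list headed Secondary outcomes is a mixed inventory. It also contains baseline questionnaires, interval history and exit questionnaires, none of which is a treatment-effect endpoint. The ASUI entry does not speak of change, and the analysis text does not name it. This reading is possible. However, the ACT and Marks AQLQ entries do not mention change either, and both are followed up. The baseline questionnaire entry states its purpose, and the ASUI entry does not. If the baseline reading is right, the listing is what needs correcting.

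**The sponsor may intend later collection.** A reader might infer from the schedule that no post-treatment ASUI will ever exist. The documents do not support so firm a prediction, because it rests on one table row and the general visit wording could take in the ASUI at later visits. A reader might also count the visit text's silence about the ASUI as further evidence of omission. It is not, since that text names no asthma questionnaire at any visit. What stands is the conditional statement: sites that follow the table will not collect it.

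**Bronchodilator spirometry may look like a second case.** The outcome list says "Spirometry with bronchodilator will be performed to measure FEV1 and FVC", while a footnote to the schedule says "V1 spirometry only will be performed pre and post bronchodilator". A reader might infer that spirometry also lacks follow-up. It does not. Spirometry is marked again at V2, V5a and V5b, so FEV1 and FVC are measured before and after treatment and the planned lung function comparison can be made. Only the comparison of values before and after bronchodilator is limited to V1.

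**The consequence is modest.** Diaries, the ACT and the Marks AQLQ still measure symptoms, control and quality of life on treatment, and the trial is sized on methacholine responsiveness. This is correct and limits the weight of the point.

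**Conclusion.** The outcome list and the schedule disagree about the ASUI and must be reconciled. If the schedule is followed as written, there are no post-randomization ASUI scores in any of the 40 participants, against three scheduled per participant for each of the ACT and the Marks AQLQ. No treatment effect on the ASUI can then be estimated by any method in the plan.

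This rests on two assumptions: that the table as printed is what sites will use, and that no instruction outside these documents adds the ASUI to later visits. The conclusion is confined to this one secondary outcome. It does not extend to FEV1 or FVC, and it does not touch the primary analysis or the sample size. It is worth correcting because the loss would be complete for that instrument and the correction is small.

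**What to change.** Mark the ASUI in the Outline of Study Visits at V2, as the baseline covering the two-week run-in, and at V5b, as the end-of-study value. Name the three instruments in the text for each visit where they are given, so that the text and the table agree. V3 and V4 could be added to match the ACT, but the pre-post and end-of-study comparisons do not require them.

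The cost is one short questionnaire at two visits where the ACT and the Marks AQLQ are already completed, plus a schedule amendment. No extra visit is needed.

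If the ASUI was intended only to describe participants at entry, leave the schedule unchanged, remove the ASUI from the secondary outcomes, and list it as a baseline characteristic. That costs only a change of text.
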